2. Admission to the **Intensive Care Unit (ICU) for more than 48 hours**.
3. Availability of **chest CT imaging data**.

Exclusion Criteria

1. Patients aged <18 years.
2. Patients with incomplete medical records.
3. Absence of chest CT imaging or presence of technically inadequate/uninterpretable chest CT images.

Sample Size and Data Partitioning

This study is designed as a multicenter, large-sample, retrospective observational study and plans to include a total of 400 patients with ARDS who meet the eligibility criteria. Of these, 300 cases will be contributed by the primary institution and Sub-center 1, and 100 cases by Sub-center 2.

The study does not involve conventional experimental or control groups. Instead, cases will be partitioned into three datasets according to the model development workflow:

Training set: 276 cases (approximately 80% of the combined cases from the primary institution and Sub-center 2), obtained through stratified random sampling to preserve the distribution of mild, moderate, and severe ARDS;

Internal validation set: 69 cases (approximately 20% of cases from the same two centers), used to monitor overfitting and optimize model hyperparameters;

External test set: 55 cases, all derived from Sub-center 1 and entirely independent of the model development process, used to evaluate model generalizability.

Primary Outcome Measures

The primary outcomes of this study focus on the overall effectiveness of the proposed AI-based framework across three key clinical tasks:

(1) Accuracy of ARDS severity classification, defined as the agreement between model-predicted ARDS severity (mild, moderate, or severe) and the reference clinical classification based on the 2023 global ARDS criteria, assessed using chest CT images obtained within 24 hours of ICU admission;

(2) Treatment plan matching rate, defined as concordance between model-recommended and actual clinical management across five intervention modalities (mechanical ventilation, high-flow oxygen therapy, non-invasive ventilation, prone positioning, and neuromuscular blockade), evaluated at the time of index chest CT acquisition;

(3) Accuracy of 28-day in-hospital mortality prediction, defined as the ability of the model to predict all-cause in-hospital mortality within 28 days of ICU admission.

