Chest CT images for all enrolled cases were exported from the hospital Picture Archiving and Communication System (PACS) in DICOM format. To minimize inter-scanner variability, all non-contrast CT images underwent standardized preprocessing. Using Python (version 3.9.13) and the open-source SimpleITK library (version 2.2.1), all images were converted to NIFTI format. Subsequently, each image was normalized to arrays with a uniform mean and standard deviation to reduce distributional differences across scanners. Following preprocessing, the images were fed into the deep learning (DL) model.

For dataset partitioning, the “createDataPartition” function from the *caret* package was used to perform stratified random sampling, assigning 60% of the data to the training set, 20% to the validation set, and the remaining 20% to the test set. The training set was used to fit the machine learning model, the validation set to select the best-performing model, and the test set to evaluate the final model performance.

Construction of a Deep-Learning Lung Segmentation Model

This study focuses on chest CT images with the lung as the organ of interest; therefore, the lung will be defined as the region of interest (ROI) for the deep-learning (DL) model. We plan to develop a U-shaped Transformer-based model for lung segmentation, with target classes including lesion regions, the whole lung, individual lobes, and all bronchopulmonary segments.

The U-Net architecture is widely used for medical image segmentation and comprises an encoder, a decoder, and skip connections. The encoder extracts local image features through successive convolutional operations and employs down-sampling to progressively expand the network receptive field. Conversely, the decoder upsamples processed features back to the original image resolution to enable pixel-level semantic inference. Skip connections fuse features from corresponding encoder and decoder layers, ensuring comprehensive feature maps that preserve precise spatial information alongside high-level semantics, which is critical for accurate segmentation. A Transformer can serve as the backbone within the U-Net encoder/decoder blocks; by using global attention mechanisms, it captures long-range dependencies and, in principle, attains a global receptive field.

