The sample size was preliminarily estimated using the event-per-variable principle. The mortality prediction component is designed to include no more than 15 candidate predictors in the final multivariable logistic regression model. Following the commonly accepted criterion of at least 10 outcome events per predictor, a minimum of 150 death

events is required to ensure model stability and interpretability. Based on historical data from the participating centers, the in-ICU mortality rate among patients with ARDS is approximately 37.5%. Accordingly, the total target sample size for this study is estimated to be approximately 400 patients.

Statistical Analysis Plan

All eligible cases will be stratified and randomly sampled at an 8:2 ratio within Shanghai General Hospital and its affiliated centers to form the model training set and internal validation set. Cases from an additional participating center will be reserved as an independent external test cohort.

Model performance will be evaluated for three predefined tasks: ARDS severity classification, treatment strategy prediction, and mortality risk prediction. Performance metrics will include accuracy, balanced accuracy, area under the receiver operating characteristic curve (AUC), precision–recall curve analysis, and the Brier score. During model development, five independent repeated experiments will be conducted, and performance will be reported as mean values with standard deviations.

For comparative performance assessment, results from the five independent experiments will be compared using two-sided Wilcoxon rank-sum tests, with a significance threshold of 0.05. Different levels of statistical significance will be denoted using conventional symbols (e.g., “*”, “**”) corresponding to predefined P-value ranges.

To assess the association between model outputs and clinical outcomes, model-recommended intervention sets will first be encoded for agreement with actual clinical management. These agreement variables will then be incorporated into multivariable logistic regression models together with six imaging-derived anatomical features (e.g., diaphragmatic height, lung volume). Adjusted odds ratios with 95% confidence intervals will be reported, and a two-sided P value <0.05 will be considered statistically significant.

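### The 150 deaths behind the sample size are reached only by counting all 400 patients, including 55 external cases kept out of model development; the 276 training cases give about 103

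*Combined protocol and SAP*

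**What the plan says.** The Sample size estimation section uses an events-per-variable rule. It states that "The mortality prediction component is designed to include no more than 15 candidate predictors in the final multivariable logistic regression model". It then says: "Following the commonly accepted criterion of at least 10 outcome events per predictor, a minimum of 150 death" events, and describes that minimum as needed for a stable and interpretable model. With an in-ICU mortality of about 37.5% from the centers' historical data, it concludes: "Accordingly, the total target sample size for this study is estimated to be approximately 400 patients".

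Sample Size and Data Partitioning divides the same 400 patients into three sets:

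- "Training set: 276 cases (approximately 80% of the combined cases from the primary institution and Sub-center 2");
- an internal validation set of 69 cases, "used to monitor overfitting and optimize model hyperparameters";
- an external test set of 55 cases, "entirely independent of the model development process, used to evaluate model generalizability".

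The Statistical Analysis Plan repeats the 8:2 split and adds: "Cases from an additional participating center will be reserved as an independent external test cohort". The Preliminary Image Processing text describes a different division, "assigning 60% of the data to the training set, 20% to the validation set, and the remaining 20% to the test set". No section says which cases the final logistic model for mortality is fitted on.

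**The concern.** An events-per-variable rule concerns the data on which coefficients are estimated. Deaths in a tuning set or an external test set can show that a model is unstable, but they add nothing to the fit. The plan counts deaths in all 400 patients and then sets 124 of them (69 + 55) aside for other purposes, and the sample size section makes no allowance for this.

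Mortality prediction is one of the three primary outcomes, and this calculation is the only justification given for 400 patients. If the fitted model has well under 10 deaths per predictor, it fails the criterion that the plan itself set. The Brier score and calibration curves planned for later would report the consequences without supplying the missing events.

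**Working it through.** **Inputs.** At most 15 predictors, 10 events per predictor and 37.5% mortality (Sample size estimation); sets of 276, 69 and 55 (Sample Size and Data Partitioning); a 60/20/20 split (Preliminary Image Processing).

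**The plan's own figure.** Required deaths = 15 × 10 = 150. Patients = 150 / 0.375 = 400. This reproduces exactly and leaves no slack.

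**The partition.** 276 + 69 = 345 and 345 + 55 = 400. The training share is 276/345 = 80% of the development cases and 276/400 = 69% of the total.

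**Deaths outside training, at 37.5%.** External: 55 × 0.375 = 20.6. Tuning: 69 × 0.375 = 25.9. Left in training: 150 − 20.6 − 25.9 = 103.5.

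**By possible fitting set.** Expected deaths = n × 0.375; per predictor = deaths / 15; predictors allowed = deaths / 10, rounded down; mortality needed = 150 / n.

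| Fitting set | n | Expected deaths | Per predictor at 15 | Predictors allowed | Mortality needed for 150 |
|---|---|---|---|---|---|
| All cases | 400 | 150.0 | 10.0 | 15 | 37.5% |
| Training + internal validation | 345 | 129.4 | 8.6 | 12 | 43.5% |
| Training | 276 | 103.5 | 6.9 | 10 | 54.3% |
| 60% of 400 | 240 | 90.0 | 6.0 | 9 | 62.5% |

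Other readings of the 60/20/20 split also fall short. Training plus validation, 80% of 400 = 320 cases, gives 120 deaths (8.0 per predictor). Sixty percent of 345 = 207 cases gives 77.6 (5.2 per predictor).

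**Chance variation (binomial, true rate 37.5%).** The probability of at least 150 deaths is about 0.52 in 400 cases and 0.013 in 345. The probability of at least 100 deaths in 276 cases, enough for 10 predictors, is about 0.69.

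**Keeping 15 predictors.** This needs 400 fitting cases, or 400 / 0.69 ≈ 580 patients at the same training share.

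**The case against.** Five points can be made for the plan.

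1. **The fitting set is not named**, so 6.9 is one scenario and not an established result. That is fair, and the finding is best read as a range. But the most favorable set that respects the external hold-out, 345 cases, still gives only 8.6. Only all 400 reaches 10, and that would bring the external cases into fitting.

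2. **Fifteen is a ceiling and the estimate is called preliminary.** With 10 predictors in 276 cases, or 12 in 345, the rule is met in expectation. This stands, and the shortfall is claimed only at the cap. Even so, 15 is the number from which 150 and 400 were derived.

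3. **The sized model might be the treatment-agreement regression**, the one multivariable logistic model that the Statistical Analysis Plan spells out. Assuming five agreement variables plus its six anatomical features, it has 11 terms, with 13.6 events each in 400 cases, 11.8 in 345 and 9.4 in 276. On that reading there is little or no shortfall. But the sample size text ties its calculation to the mortality prediction component. The association regression is a separate analysis, could use all 400 cases, and is outside this point.

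4. **One rate is applied to every center.** The decimals do depend on that. The direction does not: with 150 deaths expected overall, the development cases reach 150 only if the external center has none.

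5. **LASSO could limit overfitting.** The Statistical Analysis Plan gives LASSO an interpretive role and does not present it as the builder of the final model.

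**Conclusion.** The concern holds. The stated sample size counts deaths that the plan's own partition makes unavailable for fitting. At 37.5% mortality and 15 predictors, the mortality prediction model would have 6.9 events per predictor on the 276 training cases and 8.6 on all 345 development cases, or 6.0 if the 60/20/20 split is applied to all 400, against the required 10.

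This rests on three assumptions: the sized model is the mortality prediction model, the external cases stay out of fitting as stated, and 37.5% applies across the sets. It is a correctable inconsistency on a primary outcome and does not invalidate the study. It should be fixed before modelling.

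**What to change.** First reconcile the 60/20/20 split with the 276/69/55 partition. Then name the fitting set and restate the calculation on it. If the 276/69/55 partition is kept, suitable wording is:

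> The final logistic model for mortality will be fitted on the 276 training cases only. At 37.5% mortality about 103 deaths are expected, which allows at most 10 candidate predictors. Before modelling, the cap will be set to the number of deaths observed in these cases divided by 10, rounded down. The 55 external cases will not be used in fitting.

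The recount matters because 100 deaths is itself only about 69% likely at the assumed rate.

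A separate point, which does not bear on the shortfall, can be settled in the same edit. The 37.5% is in-ICU mortality, whereas the outcome is in-hospital death within 28 days of ICU admission; the documents do not show which is higher. Replace it with the centers' historical rate for the actual outcome under the eligibility criteria, and set the planned cap to 276 × rate / 10, rounded down. For an assumed range of 30% to 45% this gives 8 (82.8 / 10) to 12 (124.2 / 10).

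**Cost.** A few sentences in the sample size and partition sections, one sentence in the Statistical Analysis Plan, and a historical mortality query. No extra patients are needed. The price is a smaller model, 10 predictors instead of 15. Refitting on all 345 development cases would allow 12, but the 69 cases would no longer be a separate check, and any optimism correction would have to repeat the whole pipeline, including imaging features learned on those cases.

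### The 400-patient target rests on an in-ICU death rate that is not tied to the 28-day in-hospital outcome or the eligible cohort, so the 150 required deaths are not shown for the model's own endpoint

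*Combined protocol and SAP*

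**What the plan says.** The Sample size estimation section uses an events-per-variable rule. The mortality component is "designed to include no more than 15 candidate predictors in the final multivariable logistic regression model", with "at least 10 outcome events per predictor", which leads to "a minimum of 150 death" events. The step from events to patients uses one figure. It is introduced with "Based on historical data from the participating centers" and reads "the in-ICU mortality rate among patients with ARDS is approximately 37.5" per cent. The section then gives a target of about 400.

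The outcome to be predicted is defined elsewhere. Primary Outcome Measures, item 3, is "all-cause in-hospital mortality within 28 days of ICU admission".

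The cohort is also narrower than patients with ARDS as such:
- Inclusion Criteria, item 2, requires "Admission to the Intensive Care Unit (ICU) for more than 48 hours".
- Exclusion Criteria, item 3, removes "Absence of chest CT imaging or presence of technically inadequate/uninterpretable chest CT images".
- Exclusion Criteria, item 2, removes incomplete records.

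**The concern.** The planning rate and the modelled outcome differ in place of death (ICU against hospital) and in time limit (none stated against 28 days). The eligibility limits on the cohort are not stated to apply to the historical series. That series comes with no period, numerator or denominator, so the reader cannot tell whether they do.

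What is at stake is the only sample-size justification in the plan. The plan itself treats 150 deaths as the minimum for a stable and interpretable mortality model, and mortality prediction is one of its three primary outcomes. If the event rate for the actual endpoint and cohort is not 37.5%, a ceiling of 15 predictors may break the plan's own rule of 10 events per predictor.

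**Working it through.** **Inputs from the documents**
- Maximum predictors 15, events per predictor 10, planning rate 37.5%, target about 400 (Sample size estimation).
- Training set 276 (Sample Size and Data Partitioning).
- The 28-day in-hospital death rate in eligible patients is not given, so the rates below other than 37.5% are assumptions.

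**Reproducing the plan's figure**

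Events = 15 × 10 = 150. Patients = 150 / 0.375 = 400. The arithmetic is right and leaves no margin. Even if the true rate were exactly 37.5%, the binomial chance of seeing at least 150 deaths in 400 patients is about 52%.

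**Expected events if the true rate differs**

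Expected deaths = 400 × rate; events per predictor = expected deaths / 15.

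| Assumed rate | Expected deaths in 400 | Per predictor (15) | Chance of at least 150 deaths |
|---|---|---|---|
| 30% | 120 | 8.0 | 0.1% |
| 35% | 140 | 9.3 | 16% |
| 37.5% | 150 | 10.0 | 52% |
| 40% | 160 | 10.7 | 86% |

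**Can the direction be settled from the documents?**

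- Endpoint: deaths after ICU discharge but before day 28 count in the outcome and not in the planning rate, which raises the rate. ICU deaths after day 28 do the opposite.
- The 48-hour rule, if it was not already applied to the historical series, removes both early deaths and short-stay survivors. With a share d of deaths and a share s of survivors removed, the rate becomes 0.375(1−d) / [0.375(1−d) + 0.625(1−s)]. Three assumed cases:
  - d = 10%, s = 0: 0.3375 / 0.9625 = 35.1%, about 140 deaths in 400.
  - d = 10%, s = 10%: 37.5%, unchanged at 150.
  - d = 5%, s = 10%: 0.35625 / (0.35625 + 0.5625) = 38.8%, about 155 deaths.
- CT and record completeness: the documents do not say who goes unscanned or has incomplete records, so this selection could act either way.

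The net direction therefore cannot be fixed.

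**Which patients supply the events**

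The 150 deaths are counted over all 400 patients, and the section does not say which data the logistic model is fitted to. At an unchanged 37.5%:
- All 400 used for fitting: 150 deaths, cap 150 / 10 = 15.
- Only the 276 training cases: 276 × 0.375 = 103.5, about 104 deaths. That is 6.9 per predictor at 15, or a cap of about 10.

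**The case against.** The strongest reply is that the plan claims little. It calls the estimate preliminary, both the rate and the total are approximate, and 15 is a ceiling, so a smaller model is already allowed. A fall from 10 to 9.3 events per predictor does not in itself show instability. The true rate may equal or exceed 37.5%, and the real count will be known once the retrospective cohort is assembled.

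Much of this stands. The gap is a missing derivation and not an arithmetic error. But the plan presents 150 deaths as a required minimum, and nothing in it lowers the predictor ceiling if fewer occur. That the count can be made from existing records is a reason to use it.

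A reader might also infer three stronger things that the documents do not support:
- That 37.5% describes all ARDS patients. The text says only patients with ARDS at the participating centres and is silent on restrictions.
- That requiring a usable CT lowers the death rate because the sickest cannot be moved. Nothing says why patients go unscanned, and less ill patients may also be unscanned.
- That the 48-hour rule must lower the rate. That holds only if early deaths are removed and short-stay survivors are left in.

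**Conclusion.** The point holds as a gap in justification. The endpoint mismatch is explicit in the text. The population match is unstated. With no margin in 150/0.375, the minimum of 150 deaths is not shown for the outcome the model uses. Over the assumed range of 30% to 40%, the full 400 would give between 30 fewer and 10 more deaths than the plan requires.

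It would go too far to conclude that 400 patients are too few. The documents give no 28-day in-hospital rate for the eligible cohort, so neither a shortfall nor an excess can be asserted. The size figures rest on assumed rates and, except for the 276-case figure, on all 400 patients being used for fitting. This should be corrected because the plan relies on the number and the correction is cheap.

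**What to change.** 1. Count 28-day all-cause in-hospital deaths among patients who meet every inclusion and exclusion criterion at the three centres. Report numerator and denominator.
2. In Sample size estimation, replace 37.5% with that rate and restate the expected events.
3. Replace the fixed ceiling of 15 with the smaller of 15 and the observed 28-day deaths in the data used to fit the logistic model, divided by 10. State which data those are.

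The third step makes the plan meet its own rule whichever way the rate moves. The cost is one query of existing records, a reworded paragraph and possibly fewer predictors. At 37.5% the cap stays at 15 if all 400 patients are used for fitting, but falls to about 10 if only the 276 training cases are. No extra patients are needed.

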These three outcomes collectively reflect the overall effectiveness of the model within a closed-loop framework encompassing disease stratification, treatment recommendation, and prognosis prediction.

Secondary Outcome Measures

Secondary outcomes include comparative performance improvement of the proposed model over commonly used baseline AI models; calibration performance of mortality prediction; interpretability analyses based on imaging-derived and clinical feature contributions; and assessment of the association between treatment concordance and 28-day in-hospital mortality using multivariable regression models.

Research procedures

1. Data collection

(1) Demographic and Baseline Clinical Data

Age, sex, body mass index (BMI), comorbidities (including chronic kidney disease, coronary artery disease, hypertension, diabetes, liver cirrhosis, HIV infection, etc.), primary etiology of ARDS, and receipt of mechanical ventilation, high-flow nasal oxygen therapy, or ECMO. BMI is calculated as weight (kg) divided by height squared (m^2).

(2) Physiologic Parameters

Body temperature (T), heart rate (HR), respiratory rate (RR), peripheral oxygen saturation (SpO_2), and mean arterial pressure (MAP).

(3) Laboratory Parameters

pH, partial pressure of arterial oxygen (PaO_2), fraction of inspired oxygen (FiO_2), partial pressure of arterial carbon dioxide (PCO_2), lactate (Lac), platelet count (PLT), white blood cell count (WBC), hemoglobin (Hb), serum creatinine, C-reactive protein (CRP), procalcitonin (PCT), international normalized ratio (INR), B-type natriuretic peptide (BNP), and interleukin-6 (IL-6).

(4) Ventilator or High-Flow Oxygen Parameters

Positive end-expiratory pressure (PEEP), tidal volume (TV), plateau pressure (Pplat), and flow rate (FLOW).

(5) Other Clinical Scores

Sequential Organ Failure Assessment (SOFA) score and Acute Physiology and Chronic Health Evaluation II (APACHE II) score.

2. CT Equipment and Scanning Parameters

Chest CT images included in this study were acquired from two CT scanners with the following parameters:

CT1 (64-slice): Manufacturer: Philips; Model: Brilliance; Tube voltage: 120 kV; Tube current: 1000 mA; Slice thickness: 5 mm; Slice interval: 5 mm; Pitch: 0.789:1.

CT2 (128-slice): Manufacturer: United Imaging; Model: uCTR760; Tube voltage: 120 kV; Tube current: 1000 mA; Slice thickness: 5 mm; Slice interval: 5 mm; Pitch: 0.984:1.

3. Quantitative Assessment of ARDS

Preliminary Image Processing

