For mortality risk prediction, ARDS severity classification and treatment strategy information will be sequentially added to the input features to evaluate their incremental impact on balanced accuracy and Brier score. Model calibration and discrimination will be assessed using calibration curves and precision–recall curves. In addition, least absolute shrinkage and selection operator (LASSO) regression will be applied to all structural, pathological, and intervention-related variables, and standardized coefficients will be extracted to facilitate interpretation of key risk-driving factors across different ARDS severity strata.

Ethics and Informed Consent

This study is a multicenter, retrospective, observational study involving the secondary use of previously collected clinical and imaging data. The study protocol, informed consent materials (where applicable), and all subject-related documents were submitted to the institutional ethics committee and approved prior to study initiation. The study will be conducted in accordance with the Declaration of Helsinki and relevant national and institutional regulations.

The investigators will submit periodic progress reports to the ethics committee as required. Any protocol amendments or changes related to informed consent procedures will be reported to and approved by the ethics committee before implementation, unless such changes are necessary to eliminate an immediate and direct risk to participants, in which case the ethics committee will be notified promptly. The ethics committee will also be informed in writing upon study suspension or completion.

Given the retrospective nature of the study and the use of existing identifiable data without commercial interest, a partial waiver of informed consent was approved by the ethics committee. For participants who can be successfully contacted, investigators will first provide oral information about the study and document the communication. If participants or their legal representatives subsequently return for clinical follow-up, written informed consent will be obtained. For participants who cannot be contacted, the requirement for informed consent is waived in accordance with ethical and regulatory guidelines.

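### Models are compared by a rank-sum test on five runs, with neither the runs nor the scored patients defined, and no performance metric or model difference gets an interval

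*Combined protocol and SAP*

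**What the plan says.** The Statistical Analysis Plan section states: "During model development, five independent repeated experiments will be conducted, and performance will be reported as mean values with standard deviations". For comparing models it adds that "results from the five independent experiments will be compared using two-sided Wilcoxon rank-sum tests, with a significance threshold of 0.05", and that "Different levels of statistical significance will be denoted using conventional symbols". The unit of the SD and of the test is therefore the run. Five runs for each model is an inference; the text does not say it outright.

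The comparison serves a secondary outcome, listed under Secondary Outcome Measures as "comparative performance improvement of the proposed model over commonly used baseline AI models".

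On which patients are scored, the document offers several candidates:

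- Sample Size and Data Partitioning sets 276 training cases, 69 internal validation cases that also serve for tuning, and "External test set: 55 cases, all derived from Sub-center 1 and entirely independent of the model development process".
- Preliminary Image Processing describes a random 60/20/20 split, with the final 20% used as the test set.

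The only intervals in the Statistical Analysis Plan belong to a different analysis: "Adjusted odds ratios with 95% confidence intervals will be reported". For the mortality model, severity and treatment information will be "sequentially added to the input features to evaluate their incremental impact on balanced accuracy and Brier score", again with no interval named.

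**The concern.** A claim that one model improves on another, or that a model generalizes, is a claim about new patients. Its uncertainty has at least two parts: how much a model changes when it is retrained, and which patients happened to be in the test set. Repeated runs on one fixed set of patients show only the first part. More runs would shrink the P value without adding a patient.

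Two things are at stake. First, asterisks from the run-level test could be read as evidence of superiority in new ARDS patients when they show only that two sets of runs differ on one group of patients. Second, with no interval planned, readers of severity accuracy, treatment matching and mortality prediction may not see how little 55 or 69 patients can establish. The rank-sum test is also unpaired, so it ignores that the models may share patients, seeds or splits.

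**Working it through.** **Plan's own figures.** Sample size estimation: 15 predictors × 10 events ÷ 0.375 = 400 patients. The partition adds up: 276 + 69 + 55 = 400. Both reproduce, and neither addresses the model comparison.

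**What each reading implies.**

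| What the runs share | What P and SD contain | Limitation |
|---|---|---|
| The same 55 external cases | Training variability only | Patient sampling is left out |
| The same 69 internal cases | Training variability only | As above, and these cases are also used for tuning |
| One fixed 20% test split (0.20 × 400 = 80 cases) | Training variability only | As above, and not the external set |
| A fresh random split per run | Training variability and some patient variation | Runs share overlapping patients; the external set is not compared |

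No row comes with an interval for a metric or a difference.

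**Size of the patient sampling error.** The document gives no expected accuracy or AUC, so these values are assumed.

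Accuracy p = 0.75, 95% half-width = 1.96 × √[p(1 − p)/n]:

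- n = 55: 1.96 × 0.0584 = 0.114
- n = 69: 1.96 × 0.0521 = 0.102
- n = 80: 1.96 × 0.0484 = 0.095

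Over assumed accuracies of 0.6 to 0.9, the half-width at n = 55 runs from 0.129 to 0.079.

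Mortality AUC: Sample size estimation says that "the in-ICU mortality rate among patients with ARDS is approximately 37.5" percent. That is an in-ICU rate, used here as a stand-in for 28-day in-hospital mortality. 0.375 × 55 = 20.6, so about 21 deaths and 34 survivors. The Hanley-McNeil variance is [A(1 − A) + 20(Q₁ − A²) + 33(Q₂ − A²)] ÷ (21 × 34), where Q₁ = A/(2 − A) and Q₂ = 2A²/(1 + A).

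- A = 0.75: (0.1875 + 0.7500 + 2.6518) ÷ 714 = 0.00503; SE 0.0709; half-width 0.139
- A = 0.80: (0.1600 + 0.5333 + 2.3467) ÷ 714 = 0.00426; SE 0.0653; half-width 0.128

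**What the run-level test can return.** With five runs against five there are C(10,5) = 252 arrangements, so any complete separation of the runs gives an exact two-sided P of 2/252 = 0.0079, whatever the gap. Limiting case with no between-run variation: one model is right on 42 of 55 in every run and the other on 41 of 55. The gap is one patient (1/55 = 1.8 points) and the rank-sum P is 0.008. Exact McNemar with one discordant patient gives P = 1.0.

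**False-positive rate.** This was simulated for two models of equal accuracy (0.80), five runs each, on the same 55 patients. It assumed a run-specific variance share of 5% to 50% and a between-model patient correlation of 0.3 to 0.9. The rank-sum test rejected in 52% of replicates at one end (share 5%, correlation 0.3) and 4.5% at the other (share 50%, correlation 0.9). With entirely new patients for each run it rejected in 3.7%. The document gives nothing that places this study within that range.

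**The case against.** The strongest reply is that the harm is conditional. The document does not establish that the scored patients are fixed, and even on fixed patients the inflation can be nil. A reader might infer from the simulation that the planned test has a false-positive rate near one half. The document does not support that: the figure comes from assumed variance shares and is not an expected size for this study.

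The 42 against 41 example is equally not a forecast, since it sets between-run variation to zero. With the one-patient mean gap kept and runs allowed to vary, significance occurs in about 16% of comparisons at a run SD of 1 patient, 9% at 1.5 and 7% at 2. The SAP also does not specify an exact test; a tie-corrected normal approximation gives P = 0.004 for the same data.

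A reader might also infer that the primary outcomes will be reported with an SD over runs and nothing else. The text does not go so far. It ties mean and SD to model development and leaves the reporting of external performance open. The gap is that no interval is named.

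The opposite inference, that a fresh split per run makes the test sound, is not shown either, because such runs share overlapping patients.

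Finally, the general sentence on comparing models could be meant to cover the incremental mortality comparison. That would supply a test, but still no interval.

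What stands after all this: the runs and the scored set are undefined, and patient-level uncertainty is not planned for any metric or difference.

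**Conclusion.** The concern holds in conditional form and should be fixed. On a fixed test set, the run-level P value and SD omit patient sampling error and cannot alone support improvement in new patients. Under fresh splits they answer a different question from performance on the external centre. The absence of intervals holds on every reading.

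The omitted uncertainty at an assumed accuracy of 0.75 is about ±11.4 points on 55 cases, ±10.2 on 69 and ±9.5 on 80. For mortality AUC on 55 cases it is ±13.9 points at an assumed 0.75 and ±12.8 at 0.80, with the in-ICU death rate as a stand-in. No false-positive rate should be attached to the planned test.

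The rank-sum test itself serves a secondary outcome and does not affect the sample size. The missing intervals also concern the metrics for the three primary outcomes.

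**What to change.** 1. State what varies between the five experiments and which set each metric is scored on. Make this consistent with a single partition, after reconciling Sample Size and Data Partitioning with Preliminary Image Processing.
2. Report patient-level 95% intervals for every performance metric and every paired model difference, including the incremental mortality comparison. A bootstrap over patients, with the same resampled patients used for both models, is one suitable method. DeLong is acceptable for binary AUCs of frozen predictors.
3. Base claims of generalizability on the external set. State whether inference concerns the frozen predictors or the training method; the latter also needs the runs to be resampled.
4. Drop the run-level rank-sum test and its asterisks as evidence of improvement in new patients. Keep mean with SD over runs as a description of training stability, and treat results on the tuning set as descriptive.

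The cost is SAP wording, saved per-patient predictions from each run and a short script; no new data are needed. The downside is wide intervals and fewer differences declared significant. For scale, exact McNemar on 55 cases needs at least a 6–0 split of discordant patients (6/55 = 10.9 points; P = 2 × 0.5⁶ = 0.031), because 5–0 gives 2 × 0.5⁵ = 0.0625. That limit comes from the size of the external set.
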